**Abstract:** Recently there has been compelling evidence that inflammatory bowel disease (IBD) subjects, both Crohn's disease (CD) and Ulcerative Colitis (UC), commonly have disrupted sleep, and disrupted sleep correlates with the risk of disease flare. Sleep/wake cycle, immune function, metabolism and multiple biological processes are all orchestrated by circadian rhythms. Circadian misalignment between the central circadian clock in the brain and environment has been found to contribute to a variety of metabolic and gastrointestinal tract (GIT) diseases. Yet, the prevalence and impact of circadian misalignment on IBD disease activity and GIT mucosal inflammation have not been established. The long-term objective of our research is to investigate the hypothesis that circadian malalignment worsens GIT mucosal inflammation and disease course in IBD. To test this hypothesis, we will conduct a prospective in lab study with human subjects on the impact of circadian misalignment in left sided mild to moderate Ulcerative Colitis. We will perform two circadian measures phase assessments under strictly controlled laboratory conditions at: 1) baseline, and after 2) circadian misalignment after three days of simulated night shifts in both inactive UC patients and healthy control subjects. To test the hypothesis that UC patients (compared to healthy subject controls) are less resilient to circadian misalignment we will assess: time impact of our protocol on circadian rhythms (Aim 1) by the following: phase angle of entrainment [time from dim light melatonin onset to sleep onset] (Aim1a); peripheral circadian rhythms by clock gene expression in colonic tissue from a flexible sigmoidoscopy and in subjects peripheral blood mononuclear cells (Aim1b); and colonic clock gene expression and Per2::Luc activity over 24 hours utilizing an in-vitro model of colonic organoids (Aim1c). Next, we will test the hypothesis that circadian misalignment will increase colonic permeability and mucosal inflammation in UC patients (vs. Controls) (Aim2) through the following: endoscopy score, stool calprotectin, colonic barrier (permeability, AJC proteins), and markers of systemic barrier function and inflammation (Aim 2a); adversely impacting microbial community structure/function (Aim 2b); and use 2D colonic organoid monolayers to explore ex-vivo barrier function by co-culturing with TNF- $\alpha$ /INF- $\gamma$  (Aim

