2c). The results of this innovative proposal will greatly increase our understanding of the important role circadian misalignment may have in UC disease activity and colonic inflammation, and identify new circadian regulated targets for treatment in UC.

**Objective:** The long-term objective of our research is to investigate the hypothesis that circadian misalignment worsens intestinal mucosal inflammation and disease course in IBD. Key evidence supporting this hypothesis include that disruption of circadian rhythms in the host impacts the intestinal barrier, microbiota composition, and mucosal/systemic immune function, all critical factors in the pathogenesis of IBD. Data from rodents generated by our group and others show that disruption of the light: dark cycle (a model of shift work) or genetic circadian rhythm disruption (of a core clock gene) changes the intestinal microbial community, alters the production of microbial products like short chain fatty acids (SCFAs) resulting in colonic hyperpermeability through disruption of the apical junctional complex (AJC) in colonic IECs, increased mucosal inflammation, culminating in a more pro-inflammatory state in the intestine. In humans, shift work increases susceptibility of the colonic barrier to an injurious agent like alcohol and increases systemic pro-inflammatory cytokines IL-6 and IL-1 $\beta$  and that chronic alterations in light:dark cycles in mouse models of IBD increase colitis severity and mortality. In humans with IBD, our group and others have shown that a later chronotype (Fig. 2A) and high variability in rest-activity rhythms (Fig. 2B) (both markers of circadian misalignment) are associated with worse IBD disease course, increased colonic permeability, alterations in the intestinal microbiota community (dysbiosis), and reduced colonic circadian clock gene expression. Therefore, the immediate goal of this proposal is to elucidate the mechanisms of colonic inflammation induced by circadian misalignment in UC. This will be the first comprehensive examination of human circadian rhythms in IBD.

**Hypothesis:** Circadian misalignment worsens intestinal mucosal inflammation and disease course in IBD.

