A.3. IBD is characterized by Intestinal Barrier Dysfunction and Inflammation. The intestinal barrier is the largest interface between the body and the environment and must be selectively permeable to restrict pro-inflammatory microbiota and microbial products but at the same time allow passage of nutrients, electrolytes, and water. Thus, integrity of the intestinal barrier is critical for maintaining good health. Indeed, disrupted intestinal barrier function (“leaky gut”), endotoxemia (i.e., high levels of systemic lipopolysaccharide (LPS)), and subsequent production of pro-inflammatory cytokines and reactive oxygen species are all hallmarks of IBD. In fact, fluctuations in intestinal barrier function in IBD is an established predictor of disease flare in CD and UC. Several environmental factors can disrupt the intestinal barrier function in IBD like medication, alcohol, and stress but this only occurs in a subset of individuals suggesting that resiliency of the intestine determines the impact of these environmental factors in chronic inflammatory disorders like IBD. The intestinal barrier consists of the apical junctional complex (AJC), both tight junction (TJ) and adherens junction (AJ) proteins, that links the IECs and seals the paracellular space to prevent translocation of pro-inflammatory bacteria and bacterial components such as LPS into the intestinal mucosa. IECs turnover every 4-5 days, replenished by a small population of intestinal stem cells (ISCs), and IEC regeneration and differentiation are essential to maintain barrier homeostasis. It has also been established that alterations in gut microbiota are another hallmark of IBD, and perturbation of the structure of the microbiome can disrupt the intestinal barrier and cause intestinal inflammation in IBD. Specifically, in IBD there is a decrease in bacterial diversity and temporal stability with a loss of bacteria in the Firmicutes phylum^79 and increase in Proteobacteria. It is not understood if alterations in the intestinal microbiota are the cause of or result from increased intestinal permeability and inflammation, but IBD is characterized by both barrier dysfunction and dysbiosis. Disruption of central or peripheral circadian rhythms is sufficient to impact both the intestinal barrier and the microbiota; therefore, it is important to determine if circadian misalignment is sufficient to induce changes in the GIT that promote intestinal inflammation and UC disease flare.

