In addition, subjects will provide basic demographic data, UC history if appropriate, UC disease activity status as detailed further above, and the Munich Chronotype questionnaire. All subjects will complete a validated 3-month food frequency questionnaire (FFQ) to collect dietary information (1). 40 participants (Specific Aims 1-2) will be enrolled for the within-subject prospective in-laboratory study protocols. Participants will be young (18-50 y), healthy, non-diabetic, non-obese, Caucasian/African American/Asian and non-Hispanic/Hispanic in ratios consistent with the population of Chicago, and without medication use (excepting oral contraceptives) for HC. HC and UC subjects will be matched according to age ( $\pm 3$  years), sex, race, and BMI ( $\pm 3$  kg/m^2). UC subjects will be on stable medications with no recent use of prednisone or antibiotics for the last 3 months. After signing an informed consent, the subject will fill out questionnaires, start a food diary, and sleep diary, and have 2 weeks of wrist actigraphy before their seven-day in lab session in the Clinical Chronobiology Center (CCC). Since participants will be in the sleep lab for 7 days and isolation can cause an increase in depression and anxiety, a normal psychological evaluation is part of the inclusion criteria for this study. This will be determined based on how participants respond on the BDI and STAI questionnaires, which assess depression and anxiety. The study physician will review the questionnaire responses and evaluate if the participant will feel comfortable staying in the lab for 7 days.

**Subject Characteristics:** We will recruit (1) 20 HC subjects without any medical illnesses (2) 20 subjects with biopsy proven UC, inactive (Mayo Score  $\leq 2$ ) on stable medications and no disease flares for  $> 3$  months. HC and UC subject will be matched according to age ( $\pm 3$  years), sex, race, and BMI ( $\pm 3$  kg/m^2).

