**Sample Size Analysis:** All power estimates were computed using R package pwr, and we assume a Type I error rate of 0.05 and a 2-sided test for all analyses. Power estimates were derived from the data from my prior K grant. The primary endpoints of this study will be phase angle/DLMO (Aim 1) and colonic permeability (13-24h urinary sucralose) (Aim 2). For Aim 1, we found a  $\sim 2$ h phase advance in DLMO in NW compared to DW at -0.2 (SD=2.1) compared to -4.34 (SD=3.8), respectively. With a sample size of 20 in each group (10 men/10 women), this

provides an 86% power to detect differences in DLMO, but 98% power if sex is pooled. For Aim 2, we found a 40% increase in colonic permeability in night shift workers compared to day workers after moderate alcohol consumption at 0.57 compared to 0.11 (SD=0.20). With 20 subjects, this will give us a 84% power to detect a difference in colonic permeability between the two groups for each sex and if sex is pooled will give us a 97% power with a two-sided two-sample t-test at alpha=0.05 level. These conservative estimates provide a good estimate of the power to detect differences in phase angle and colonic permeability between UC patients before and after simulated night shifts. We anticipate we will have nonparametric data and will use the Wilcoxon match-pair test for analysis of colonic permeability, inflammatory cytokines, and markers of endotoxemia. Order effects will be used as a covariate in multivariate analysis with analysis of variance (ANOVA) and linear regression as indicated. Microbiota data analysis is described above. Non-parametric analysis of actigraphy data will be analyzed with the nparACT package. In our periodogram analysis of time series data we will use Fast Fourier Transform Non-linear Least Squares (FFT-NLLS), a nonlinear least-squares algorithm of a times series typically used for luminescence data (149) and analyzed with Biodare software (150). Data will be presented as mean  $\pm$  SEM for variables that can be considered normally distributed (or median and range for variables not normally distributed). All analyses will use R (v.3.2.5), Biodare 2, and SPSS (SPSS Inc., Chicago, IL).

**Inclusion Criteria:** *Study will include individuals that are;*

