**Healthy Controls**

1. History of drug abuse, gastrointestinal (GI) surgery, GI diseases, or systemic diseases such as renal (creatinine $>1.2$  mg/dl), liver, cardiac, or diabetes (Hgb-A1c $>8\%$ )
2. Antibiotic use within last 12 weeks
3. Shift work in the last 6 months
4. Use of probiotic supplement except yogurt in last 4 weeks.
5. Atypical American diet with daily fiber  $\geq 16$  grams or daily saturated fat  $\leq 11$  grams by Food Frequency Questionnaire
6. Chronic use of NSAIDS. A washout period of 3 weeks is needed before the subject could be enrolled into the study.
7. Chronic Alcohol use. A washout period of 3 weeks is needed before the subject could be enrolled into the study.
8. Significant Depression (score  $\geq 14$  BDI)
9. Significant Anxiety (score  $\geq 40$  STAI)
10. Regular use of medications that affect intestinal permeability, intestinal motility and/or endogenous melatonin including metoclopramide, NSAIDs, antibiotics, beta blocker, psychotropic medication, hypnotics and exogenous melatonin products during 4 weeks prior to the study
11. People who crossed more than 2 time zones in the previous month
12. Inability to sign an informed consent form.
13. Have children Under 6 Months

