**Ulcerative Colitis:**

1. Patients with other forms of colitis such as Crohn's disease (CD) or indeterminate colitis
2. Patient with active UC (Mayo  $> 2$ )
3. Pancolonic UC (colitis past the splenic flexure, Montreal E3))
4. Gastrointestinal surgery
5. Other GI diseases or systemic diseases (cardiac, renal failure, cirrhosis)
6. Shift work in the last 6 months
7. Antibiotic use within last 12 weeks
8. Patients who have used anti-diarrheal agents such as Lomotil or Imodium within 3 days of the study
9. Prednisone use the last 30 days
10. Significant Depression (score  $\geq 14$  BDI)
11. Significant Anxiety (score  $\geq 40$  STAI)
12. Use of probiotic supplement in last 4 weeks except yogurt.
13. Intentional change in diet.

14. Chronic use of NSAIDS. A washout period of 3 weeks is needed before the subject could be enrolled into the study. Low dose aspirin is allowed.
15. Chronic Alcohol use. A washout period of 3 weeks is needed before the subject could be enrolled into the study.
16. Have children under 6 months

**Subject Recruitment:** All Human UC subjects will be recruited at the RUMC Digestive Disease Clinic and the Rush Crohn's and Colitis Center by the PI or Clinical Coordinator. Healthy control subjects will be recruited by established recruiting methods, which we have successfully used over the past ten years, including notices to local organizations and internet, newspaper, and radio advertising. Based on our experience, of the initial calls made by potential subjects, 15% remain interested in the study after they are informed of study procedures. Of these individuals, 70% pass an initial telephone screening (in which questions are asked about medical condition, current medication use and work and travel history). Of those remaining individuals, 33% pass the medical and psychological screening (described below), and of these, 70% complete the study.

In this study we will recruit 40 Human Subjects in the following two groups:

- 1) Ulcerative Colitis (UC) (n=20).
- 2) Healthy Controls (HC) (n=20).

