**Figure 1. Outcome Measures**

Aims	Outcome Measure	Test	Assessment	Statistical Test
Aim 1	Primary	Phase Angle of entrainment (DLMO – sleep onset)	Baseline	ANOVA
			Misalignment	
	Secondary	Clock gene expression in PBMCs	Baseline	Cosinor Analysis, Mixed Model ANOVA
			Misalignment	
Aim 2	Secondary	Urinary Melatonin	Baseline	Wilcoxon signed-rank test
			Misalignment	
	Exploratory	Clock gene expression and Per2::LUC in Colonic Organoids	Baseline	Cosinor Analysis, FFT-NLLS
			Misalignment	
Aim 2	Primary	Intestinal Permeability (i.e. 12-24 h Urinary Sucralfate)	Baseline	Mann-Whitney U test
			Misalignment	
	Secondary	Mayo Score (Endoscopy)	Baseline	Wilcoxon signed-rank test
			Misalignment	
	Secondary	Stool Calprotectin	Baseline	Wilcoxon signed-rank test
			Misalignment	
Aim 2	Secondary	Serum cytokines (IL-6, TNF- $\alpha$ )	Baseline	Repeated measures ANOVA
			Misalignment	
	Secondary	Fecal Microbiota	Baseline	Principal Coordinate Analysis
			Misalignment	
Aim 2	Secondary	Serum LBP, LPS, zonulin, sCD14, metabolomics	Baseline	Repeated measures ANOVA
			Misalignment	
	Exploratory	TER in 2D Colonic	Baseline	ANOVA

		Organoids with ex-vivo TNF- $\alpha$ /INF- $\gamma$	Misalignment	
Exploratory		RNA seq of Colonic Organoids	Baseline	JTK Cycle
			Misalignment	

**Safety and Adverse Events:** We have identified five key potential risks to human subjects in this study:

1. Risk to Confidentiality and Record-Keeping of patient personal health information (PHI).
2. Risk of potential side effects associated with Phlebotomy (blood draw).
3. Risk of potential side effects associated with Sigmoidoscopy and Colonic Biopsy.
4. Risk of potential side effects associated with completion of the Questionnaires.
5. Risk of potential side effects associated with in lab study

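### Low-dose aspirin is permitted in UC subjects but not in healthy controls: a small, avoidable one-group exposure in any UC-versus-control comparison of urinary sucralose levels

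*Combined protocol and SAP*

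**What the plan says.** The two exclusion lists treat NSAIDs differently.

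- **UC list, item 14.** Chronic NSAID use is excluded, with a 3-week washout, and then: "Low dose aspirin is allowed".
- **Control list, item 6.** The same NSAID rule and washout, with no aspirin exception.
- **Control list, item 10.** Also excluded: "Regular use of medications that affect intestinal permeability, intestinal motility and/or endogenous melatonin including metoclopramide, NSAIDs", followed by other drug classes. The UC list has no counterpart.
- **Research Design, repeated in Data Analysis Methods.** Controls are to be "without medication use (excepting oral contraceptives) for HC".

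The outcome concerned is 12-24 h urinary sucralose, listed under Study Outcomes as a primary measure for Aim 2. The Abstract frames Aim 2 as a hypothesis about UC patients against controls. Figure 1 gives a Mann-Whitney U test for the row labelled "Intestinal Permeability (i.e. 12-24 h Urinary Sucralfate" (read here as sucralose, as in Study Outcomes). The Sample Size Analysis instead says the study "will use the Wilcoxon match-pair test for analysis of colonic permeability". The plan therefore does not settle whether groups are compared on levels or on changes.

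**The concern.** The plan permits in one group, and bars in the other, a drug that it treats as an exception within its own NSAID rule. Its control list names NSAIDs among drugs that affect permeability. Background A.3 says: "Several environmental factors can disrupt the intestinal barrier function in IBD like medication", though it adds that this occurs only in a subset of individuals. The reference cited there has acetylsalicylic acid and intestinal permeability in its title. The title is all the documents give, so no result or dose can be taken from it.

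Matching does not include medication, and no adjustment or sensitivity analysis for aspirin is planned. In a comparison of UC and control sucralose levels, any aspirin effect would be counted as a disease difference. UC maintenance treatment also differs between the groups, but it belongs to the condition under study. Aspirin is not named anywhere as a UC treatment, so this part of the imbalance can be avoided.

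**Working it through.** **1. Does another rule remove the asymmetry?** No. The Diet Assessments paragraph prohibits prescribed drugs subject to exceptions it does not name. Its requirement that volunteers be drug-free cannot mean free of all medication, because UC subjects must be on stable medication.

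**2. The plan's own figure.** The Sample Size Analysis gives 0.57 against 0.11 with SD 0.20, so the planning effect is (0.57 - 0.11)/0.20 = 2.3 SD. It states 84% power per sex and 97% pooled. A two-sided two-sample t-test at 2.3 SD gives 99.8% at 10 per group and about 100% at 20 per group, so the stated powers do not reproduce. That is a separate matter; only the SD and the planning effect are used below.

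**3. Shift in the UC mean.** The documents give no prevalence or effect for aspirin. Assume k = 0 to 2 users among 20 UC subjects, each shifted by d = 0.5 to 2 SD. The mean shift is k × d / 20.

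| k | d (SD) | Shift (SD) | Shift (units, × 0.20) |
|---|---|---|---|
| 0 | any | 0 | 0 |
| 1 | 0.5 | 0.025 | 0.005 |
| 1 | 1 | 0.05 | 0.01 |
| 2 | 1 | 0.10 | 0.02 |
| 2 | 2 | 0.20 | 0.04 |

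**4. Type I error for a comparison of levels.** Mann-Whitney, 20 against 20, two-sided 5%, critical U = 127 (exact size 4.91%). Simulation used normal data and 400,000 runs (Monte Carlo margin about 0.07 percentage points), with no true group difference apart from aspirin.

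| Users | d = 0.5 | d = 1 | d = 2 |
|---|---|---|---|
| 0 | 4.86% | 4.86% | 4.86% |
| 1 | 4.87% | 4.89% | 4.92% |
| 2 | 5.01% | 5.40% | 6.09% |

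**5. Power at 2.3 SD.** It is at least 99.99% in every case run, including two users each shifted by 2 SD against the effect.

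**6. Comparisons of change.** Write TD1 and TD2 for the baseline and misalignment test days. A constant aspirin effect c gives (TD2 + c) - (TD1 + c) = TD2 - TD1, so nothing remains. If the effect were larger at TD2 by e SDs of change, the mean change would move by k × e / 20. With e = 1 and one or two users, that is 0.05 to 0.10 SD of change. The documents give no SD of change.

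**The case against.** The strongest case against raising this is that nothing measurable may follow from it. Participants are aged 18 to 50, and cardiac disease is excluded in the UC group, so there may be no aspirin users at all. With one user the error rate does not move. The 6.1% needs two users each shifted by 2 SD, which is 0.40 units, or 0.40/0.46 = 87% of the planning difference. The exception was written deliberately for low dose. The design is largely within-subject, where a stable effect cancels. UC subjects also take aminosalicylates and, in some cases, biologics, so removing aspirin leaves the larger drug difference in place.

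All of this stands and sets the size of the point. It does not remove the printed asymmetry, and Figure 1's unpaired test leaves a comparison of levels open.

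A reader might infer three stronger things that the documents do not support.

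- **That aspirin biases the Aim 2 result in a known direction, or costs power.** No size or direction is given for low-dose aspirin on 12-24 h sucralose, and power at the planning effect does not move.
- **That the before-and-after comparison is also confounded.** The Objective says "shift work increases susceptibility of the colonic barrier to an injurious agent like alcohol", so an aspirin effect that grows under misalignment cannot be ruled out. The statement's example is alcohol, and extending it to low-dose aspirin would be speculation.
- **That deleting the sentence would make the contrast one of disease alone.** It would not, because maintenance drugs still differ.

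**Conclusion.** The point holds as a minor, inexpensive improvement. The eligibility rules create a one-group exposure to a drug from a class the plan itself links to permeability. It matters for UC-versus-control comparisons of sucralose levels, and not for within-subject or change comparisons if the effect is stable and additive. Under the assumed 0 to 2 users and shifts of 0.5 to 2 SD, the UC mean moves by 0 to 0.20 SD (0 to 0.04 units) and type I error reaches at most about 6.1%. Both ranges are assumptions, so the true size cannot be derived from the documents. It does not threaten the Aim 2 conclusion.

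**What to change.** **Preferred.** Delete the low-dose aspirin sentence from UC item 14 and exclude UC candidates who take it regularly. State that nobody is to stop prescribed aspirin in order to qualify. Deletion alone would bring prescribed aspirin under item 14's 3-week washout, which is a clinical cost with no matching benefit. Keep UC maintenance drugs permitted.

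*Cost:* a few lost candidates. Subject Recruitment gives 33% passing medical and psychological screening and 70% of those completing. If these rates apply to UC and 20 completers are wanted, 20/0.70/0.33 = 86.6, or about 87 candidates reach that screening. Losing 5% or 10% as aspirin users (assumed, matching one or two of 20) gives 86.6/0.95 = 91.1 or 86.6/0.90 = 96.2, so about 96 at the top of the range.

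**If the allowance is kept.** Use the medication information already gathered at screening (the telephone screen asks about current use). Pre-specify one sensitivity analysis of sucralose that omits aspirin users and their matched controls.

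*Cost:* one extra analysis. Omitting one or two pairs raises the difference detectable with 80% power (two-sample t-test) from 0.91 SD at 20 per group to 0.93 SD at 19 or 0.96 SD at 18, in that analysis only.
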